The efficacy of ablation is also limited. In multicenter trials approximately ½ of patients experience a recurrence of VT during follow-up, although the VT frequency is reduced for many. VT ablation is superior to escalating AAD therapy in patients with a prior myocardial infarction who have VT during AAD therapy, however, many continue to require AADs following ablation.^{11,13,35} The acute effect of catheter ablation is typically assessed using programmed stimulation to induce VT at the end of the procedure. **Figure 3** presents the breakdown of ventricular arrhythmias that were acutely inducible following VT ablation by [name] and colleagues (N=165 patients).³⁶ These data support the design of a clinical trial proposing to study ventricular arrhythmias that remain inducible in patients following a VT ablation procedure. Monomorphic VT that lasted >30 seconds was induced in 38 patients, VF was induced in 9 patients, and non-sustained VT (NSVT) was induced in 34 patients. These arrhythmias are not ablated because an ablation target site could not be found or they do not match a VT that had been observed clinically (e.g. NSVT, VF, monomorphic VT that is much faster than spontaneously occurring VT), and therefore predict a lower risk of VT recurrence.³⁷ However, a major finding of this study was that inducible NSVT was a marker for VT recurrence. Similarly, inducible polymorphic VT/VF, and rapid monomorphic VTs are associated with an increased risk of spontaneous VT in other studies.^{37,38} Thus inducibility of these arrhythmias indicates the continued presence of an arrhythmia substrate which lends itself to the electrophysiologic assessment of therapy, particularly in paired, blinded assessments. In our proposal we selected a duration of 10 seconds as our definition for an inducible ventricular arrhythmia, as this has been used in other studies of drug assessment and reduces the likelihood of VT/VF requiring cardioversion.³⁹

1.6 The effect of dantrolene on muscle strength and respiratory mechanics.

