Research by our group and others has focused on the role of diastolic calcium (Ca) leak via the RyR2 channel as a cause of delayed afterdepolarizations (DADs) and polymorphic VT in rare genetic disorders such as catecholaminergic polymorphic VT (CPVT).^{44,45} This led to the discovery that drugs which stabilize the RyR2 channel eliminate DADs and polymorphic VT in CPVT; this includes not only the experimental probe drug ent-verticilide but also clinically used agents such as flecainide and its derivatives and dantrolene, which is being studied here.^{46,47} The recognition that structural heart disease results in post-translational modification of RyR2 and diastolic Ca leak is consistent with the idea that Ca leak is also involved in generating VT/VF in more common diseases.⁴⁸⁻⁵¹ Accordingly, the **overarching hypothesis** to be tested is that RyR2 hyperactivity in patients with structural heart disease drives proarrhythmic changes in refractoriness and conduction, and decreases cardiac contractility, which promotes VT/VF (**Figure 1**).

Despite the success of flecainide to treat CPVT, it is relatively contraindicated in patients with structural heart disease because of its Na-channel inhibition. Dantrolene, a currently available drug that inhibits RyR2, but has no Na or K channel activity, will be used as a tool to study RyR2 modulation. Here, we propose a randomized controlled trial of dantrolene versus placebo in patients with structural heart disease referred for VT ablation to evaluate electrophysiologic, hemodynamic, and arrhythmia prevention endpoints. Dantrolene's inhibition of RyR1 will also be studied to define its effect on muscle and respiratory strength in this clinical population, which will be important if dantrolene is to be considered for repurposing as an antiarrhythmic drug. Accordingly, we propose the following Specific Aims:

Aim 1: To conduct a randomized, placebo-controlled trial of dantrolene to study the effect of RyR inhibition on cardiac electrophysiology, hemodynamics, arrhythmia inducibility, muscle strength, and respiratory mechanics in patients with structural heart disease referred for VT ablation.

Aim 2: To explore the pharmacokinetic/pharmacodynamic relationship of I.V. dantrolene and its short-term effect on cardiac electrophysiology, hemodynamics, and muscle and respiratory strength.

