4.0 INCLUSION/EXCLUSION CRITERIA (TABLE 1)

Inclusion
≥18 years of age
Able to give written, informed consent
Referred for catheter-based VT ablation or PVC ablation
Structural heart disease (LVEF < 50%, history of prior myocardial infarction, cardiac sarcoid or valvular heart disease)
Permanent pacemaker or implantable cardioverter defibrillator
Exclusion
Mechanical ventricular support (e.g. LVAD, ECMO)
NYHA class IV heart failure
LVEF <20%
Severe renal insufficiency (GFR<30 mL/min)
Morbid obesity (BMI≥ 40 kg/m ²)
Chronic liver disease (Child Pugh class A-C)
Current use of calcium channel blockers
Neuromuscular disorder (e.g. muscular dystrophy)
Chronic obstructive pulmonary disease or restrictive lung disease requiring oxygen therapy or history of intubation
Pregnant or nursing
History of dysphagia

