5.0 ENROLLMENT AND RANDOMIZATION

Table 1. Eligibility Criteria

Recruitment and informed consent: Eligible subjects will be identified by either: 1) Arrhythmia Clinic nurses or physicians will contact a member of the study team if they are scheduling an eligible subject for VT ablation or PVC ablation, or 2) the study coordinator will review the EP Lab schedule for VT and PVC ablation cases and screen their medical record for eligibility. The study coordinator will then request the clinical staff to obtain permission from the patient to contact them about research. If the patient agrees, a member of the study team will approach the patient in person in Arrhythmia Clinic, Vanderbilt University Hospital, or by phone prior to ablation. Information describing the study, why the research is being done and what will be learned will be provided. The risks as described in this protocol will be delineated. The benefits will be described as general scientific knowledge, along with potential treatment advances. No direct immediate benefit to the subjects is anticipated. The patient will be given either a hard or electronic copy of the informed consent document. At least 24 hours will be given for the patient to consider participation after which the study coordinator will recontact the patient. If the patient desires to participate, informed consent will be documented with the subject's signature using the IRB-approved consent form for this protocol. This will occur in Arrhythmia Clinic or Vanderbilt University Hospital. If participation is being discussed with the patient by phone, a tentative agreement to participate will be obtained and the study coordinator will meet the patient on the morning of the procedure at Vanderbilt University Hospital to sign the informed consent document.

Randomization: 84 participants will be randomly assigned in a 2:1 ratio to treatment (dantrolene) or control (placebo). A computer-generated randomization list will be prepared by the study statistician using the stratified permuted block randomization, where block size varies randomly from 4 or 6 to ensure overall balance across treatment arms. Randomization will be stratified by 1) amiodarone use within the past 21 days defined as chronic oral use or >5 grams cumulative dose including ongoing use and 2) planned PVC vs. VT ablation. The study statistician will generate the allocation schedule but will remain blinded to the treatment assignment.

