between the two study arms. For instance, if the pre-drug PA diastolic pressure measurements have a SD of 4 mmHg, we will have 80% power to detect a difference of +/- 2.4 mmHg in PA diastolic pressure. If the pre-drug average PA diastolic pressure is 12 mmHg, this means a 20% change in the treatment arm is detectable assuming there is no change in the control arm. Each primary endpoint will be tested at the two-sided 5% significance level.

Inducibility Endpoints: The primary hypothesis in Aim 3 tests whether RyR2 inhibition with dantrolene reduces the susceptibility to ventricular arrhythmias. Susceptibility to ventricular arrhythmias is measured by testing the inducibility of VT/VF using programmed ventricular stimulation.

Primary Analysis Aim 3:

Inducibility of Ventricular Arrhythmias: Ventricular arrhythmias are defined as monomorphic or polymorphic VT, or VF. The primary endpoint is either a sustained hemodynamically stable ventricular arrhythmia of ≥ 10 seconds duration or an unstable ventricular arrhythmia requiring termination (with pacing or defibrillation), or two episodes of non-sustained ventricular arrhythmia defined as an episode lasting 3-9 seconds. To maximize statistical power, the primary analysis utilizes an ordinal endpoint that measures the relative inducibility based on the stage of the induction protocol and the arrhythmia induced (**Table 5**). Multivariable regression models are built. Univariable logistic regression modeling will be used to test whether treatment with dantrolene is associated with the category of inducibility (ordinal endpoint) measured post-study drug with adjustment for the stage of inducibility measured pre-study drug. Multivariable modeling includes additional adjustment for age (continuous), sex, amiodarone exposure (yes/no), change in beta-agonist exposure, and time from start of drug to post-drug stimulation protocol. Models will be evaluated for goodness-of-fit, and internally validated for calibration/discrimination with bootstrap.

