Secondary Analyses Aim 3: A binary endpoint of inducibility (yes/no) is analyzed using logistic regression with the same covariate adjustment described for the primary analysis. Another secondary analysis tests the idea that RyR2 inhibition with dantrolene may alter inducible ventricular arrhythmias due to changes in conduction and refractoriness and hemodynamic improvement. An ordinal variable defining the cardiac rhythm stability class is analyzed (**Table 6**) using multivariable ordinal logistic regression. A secondary analysis will explore all the ventricular arrhythmia susceptibility endpoints for an interaction between cardiomyopathy type (ischemic versus non-ischemic) and treatment with dantrolene. Definitions: 1) Stable monomorphic VT is mean arterial pressure at 10 seconds (MAP_{10}) or immediately prior to termination of >50 mmHg; 2) Unstable VT is MAP_{10} or prior to termination of <50 mmHg; 3) Pleomorphic VT is more than one QRS morphology for 3 or more consecutive beats during the same VT episode; and 4) Polymorphic VT is a continually changing QRS morphology.⁵⁴

Sample Size and Power Aim 3: Primary Endpoint: The sample size selected for this trial was calculated to adequately power the analysis of the inducibility endpoint in Aim 3 which is an ordinal variable (Table 5). With $N=84$ patients (randomized to placebo and treatment in 1:2 ratio) with an expected 50% of patients in the placebo arm non-inducible, and 10% in each of the other categories, the study will achieve 80% power to detect an odds ratio (OR) of 0.3 at the two-sided significance level of 5%. With an anticipated 20% withdrawal rate prior to study drug, up to a total number of 105 patients will be enrolled in the study to ensure statistical power. Secondary Endpoints: 1) The binary status of inducibility (yes/no). With an effective sample size of 84, the study provides 80% power to detect an OR of 0.25, and a 70% power to detect an OR of 0.3 at the two-sided significance level of 5%.

Assessment of Safety (Aim 3): An interim analysis will be performed by the DSMB when 50% of the target enrollment is reached to test for an association between dantrolene or placebo and significant adverse events/harm. In order to preserve statistical power for the secondary analyses, the interim analysis will not include early stopping rules for efficacy. Although none of our Phase I pre-clinical or clinical data have raised

Table 5. Ordinal Inducibility Endpoint

	Category	

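### The Aim 3 models omit the PVC-versus-VT randomisation stratum, and the single 50% placebo rate behind N=84 is neither sourced nor stated for the mixed population

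*Combined protocol and SAP*

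**What the plan says.** - Section 10.0 (Sample Size and Power Aim 3) says that N was chosen for the ordinal inducibility endpoint. It assumes 84 patients allocated 1:2, "with an expected 50% of patients in the placebo arm non-inducible", and 10% in each other category, and claims 80% power at OR 0.3 (two-sided 5%). For the binary secondary endpoint it claims 80% at OR 0.25 and 70% at OR 0.3. It cites no source for the 50% and does not mention PVC patients.
- Section 2.0 describes the trial this way: "we propose a randomized controlled trial of dantrolene versus placebo in patients with structural heart disease referred for VT ablation". Table 1 in section 4.0 is wider: "Referred for catheter-based VT ablation or PVC ablation".
- Section 5.0 stratifies randomisation on recent amiodarone use and on "planned PVC vs. VT ablation".
- Section 10.0 (Primary Analysis Aim 3) adjusts for the pre-drug stage of inducibility. It then says: "Multivariable modeling includes additional adjustment for age (continuous), sex, amiodarone exposure (yes/no), change in beta-agonist exposure", together with time from drug to stimulation. Planned procedure is not listed. The binary analysis uses the same covariates.
- Section 1.5 gives the only post-ablation inducibility counts in the text, from 165 patients after VT ablation. Sustained monomorphic VT was induced in 38, and "VF was induced in 9 patients, and non-sustained VT (NSVT) was induced in 34 patients".

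**The concern.** A factor judged important enough to stratify on would normally appear in the model. Here amiodarone, the subject of the other stratum, appears in the Aim 3 models and planned procedure does not.

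The sizing rate raises a related question. Only patients who would be inducible on placebo can show prevention of induction, so each extra non-inducible patient leaves less room for benefit. If the 50% describes VT-ablation patients and PVC-ablation patients are less inducible, the endpoint that set N has less power than stated, and a null result would be harder to interpret.

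**Working it through.** **Cohort rate.** 38 + 9 + 34 = 81 inducible; 165 − 81 = 84; 84/165 = 50.9% non-inducible. This is close to the planned 50%.

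**Reproducing the ordinal 80%.** Inputs from section 10.0: 28 placebo, 56 dantrolene, OR 0.3, two-sided 5%. Whitehead's proportional-odds formula is power = Φ(|ln OR|·√V − 1.96), with V = n0·n1/(3N) × (1 − Σp̄³), where p̄ is the category distribution over both arms. Here n0·n1/(3N) = 28×56/(3×84) = 6.222 and |ln 0.3| = 1.204. I use six categories, because 50% plus 10% each totals 100% only with five others; with the nine others in Table 5 it totals 140%.

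- *50%/10% as the distribution over both arms:* Σp̄³ = 0.125 + 5×0.001 = 0.130. V = 6.222×0.870 = 5.413. Power = Φ(1.204×2.327 − 1.96) = Φ(0.84) = 80.0%. This matches the plan.
- *50%/10% as the placebo arm, as worded:* OR 0.3 moves dantrolene non-inducibility to 1/1.3 = 76.9%. Averaging the two arms gives 1 − Σp̄³ = 0.742 and V = 4.620. Power = Φ(1.204×2.149 − 1.96) = Φ(0.63) = 73.5%. A rank-test simulation gives 73%.

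Spreading the inducible half equally over nine categories gives 80.1% and 73.6%, so the number of categories matters little.

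**Reproducing the binary figures.** Two-proportion normal test. At OR 0.25, inducibility is 50% versus 20% and the pooled proportion is (14 + 11.2)/84 = 0.30. The null and alternative standard errors are 0.1061 and 0.1086. Power = Φ((0.30 − 1.96×0.1061)/0.1086) = Φ(0.85) = 80.2%. At OR 0.3 it is 70.0%. Both match the plan.

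**Effect of case mix.** The documents give neither the PVC share s nor the PVC non-inducible rate r, so both are assumed. With VT patients at 50%, the overall rate is (1 − s)×50% + s×r. Inducible patients are spread equally over five categories.

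| Overall non-inducible | Example mix (s, r) | Ordinal OR 0.3, rate over both arms | Ordinal OR 0.3, rate in placebo arm | Binary OR 0.25 | Binary OR 0.3 |
|---|---|---|---|---|---|
| 50% | no PVC effect | 80.0% | 73.5% | 80.2% | 70.0% |
| 55% | 25%, 70% | 78.1% | 70.3% | 77.5% | 67.5% |
| 60% | 25%, 90% | 75.6% | 66.5% | 74.0% | 64.2% |
| 65% | 50%, 80% | 72.4% | 61.9% | 69.6% | 60.3% |
| 70% | 50%, 90% | 68.2% | 56.6% | 64.4% | 55.5% |

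**Effect of adding the stratum.** In simulations with the pre-drug category already in the model, adding planned procedure gains about 0 to 3 points. Without the pre-drug category, with OR 0.3 in each stratum and half the patients PVC at 80% non-inducible, a rank test has 57% power unstratified and 60% stratified.

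**The case against.** The strongest reply is that nothing in the documents shows PVC patients to be less inducible.

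- Every participant needs structural heart disease and a pacemaker or ICD (Table 1). Section 7.0 says most ablation patients have had recent shocks or ventricular arrhythmias.
- In VT cases, inducible VT is itself ablated before the baseline stimulation (sections 6.1 and 6.2), which lowers inducibility in that group.
- A modest mix costs little: at 55% overall the loss is about 2 to 3 points.
- The 50.9% match is loose. It counts every NSVT patient, and section 1.5 does not give the duration or number of episodes. Counting only sustained VT and VF, (38 + 9)/165 = 28% were inducible. The trial endpoint requires two NSVT episodes, so a patient with one may count as a binary no.

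All of this stands, and it makes the power loss conditional. It does not explain why a randomisation stratum is missing from the model, or why one unsourced rate serves a mixed population.

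A reader might also infer that the 50% was taken from the VT cohort and kept after eligibility was widened. The documents do not say so. The pilot results under section 3.3 were not available for this check, so a pilot basis cannot be excluded, and no passage records a later widening. Nor does the section 2.0 wording show that the pooled odds ratio answers the wrong question: eligibility, randomisation, withdrawal and the modified intention-to-treat set all cover both procedures.

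**Conclusion.** The point holds in a limited form. Two things are established from the text: the Aim 3 models omit a stratification factor, and the placebo rate that fixes N has no stated source and no breakdown for the PVC-ablation patients.

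The power loss depends on an assumed overall non-inducible rate. From 55% to 70%, the ordinal loss is about 2 to 12 points on the reading that reproduces 80%, and about 3 to 17 points on the literal placebo-arm reading. The binary loss at OR 0.25 is about 3 to 16 points. It is zero if PVC patients are as inducible as VT patients.

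It would be tempting to conclude that enrolling PVC patients leaves the trial underpowered. The documents do not support that. The larger certain gap, 80% against about 73%, comes from how the 50% is read and exists with no PVC effect at all. These figures ignore the planned adjustment for pre-drug inducibility, which could change absolute power.

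**What to change.** 1. Add planned procedure (PVC versus VT) to the Aim 3 ordinal and binary models. This costs one degree of freedom and is expected to gain about 0 to 3 points of power.
2. In the Aim 3 sample-size text, say whether 50% is the placebo-arm rate or the rate over both arms. Restate ordinal and binary power over a range of overall non-inducible rates for the mixed population, such as 50% to 70%. Check the assumed rate against pre-drug inducibility pooled over arms; it is measured before dosing and can be read without arm information.
3. Optionally, report the treatment estimate with its 95% CI in the VT-ablation stratum as supportive. It will be less precise than the overall estimate.

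The cost is wording in the protocol and analysis plan, and a less favourable stated power. No extra patients are needed. The change does not restore lost power; it makes the claim accurate and the analysis consistent with the randomisation.

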6.0 STUDY PROCEDURES

6.1 VT or PVC Ablation will be Performed According to Standard-of-Care Clinical Practice

Duration (mins)	STANDARD CLINICAL PROTOCOL	RESEARCH PROTOCOL	
		EP team	Anesthesia team
---	Pre-procedure holding room		Pre-drug muscle strength (grip and NIF)
60-140*	Clinical ablation procedure completed		
5	Post-ablation EPS & inducibility	Pre-drug EPS & inducibility	NIF, tidal volume, minute ventilation, ABG
5	Post-ablation ICE survey	LVERP & conduction time testing	
5	Post-ablation hemodynamics	Pre-drug hemodynamics	
3		Study drug given	
10		PK/PD blood sampling with measurement of ECG intervals and Fick cardiac output	NIF, tidal volume, minute ventilation, ABG
5		LV ERP & conduction time testing	
5		Post-drug hemodynamics	
2		Post-drug inducibility testing	
5			
---	Procedure completed		2-hour post-drug muscle strength (grip and NIF) and ABG
5	Post-procedure care unit		

Table 2. List of peri-procedural clinical and research activities. NIF: negative inspiratory force; ICE: intracardiac echocardiogram; LVERP: left ventricular effective refractory period; PK/PD: pharmacokinetics/pharmacodynamics.

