6.2 List of Encounters Detailing the Clinical and Research Activities

Encounter 1: Enrollment and Informed Consent

- Performed by the study team in the Vanderbilt Arrhythmia Clinic or Vanderbilt University Hospital.

Encounter 2: Time of Ablation

- The participant will arrive the morning of ablation to the EP pre-op holding room and undergo standard preparations for ablation according to the clinical protocols (e.g. labs, vitals, exam, procedural consent).
- The participant will undergo baseline muscle (grip) and respiratory (NIF) strength testing in the pre-op area.
- The participant is then transported to the operating room (EP lab) where standard of care ablation is performed under the direction of the clinical team. See section 6.1 for full details.
- Research activities will begin after completion of the ablation portion of the ablation procedure. Research activities occur concurrently with clinical activities and are performed by a dedicated physician and nurse team to avoid extending overall case time.
- The clinical post-ablation EP study with programmed ventricular stimulation will serve as the baseline (pre-dantrolene) assessment of cardiac electrophysiology parameters (conduction and refractoriness) and ventricular arrhythmia inducibility. Data analyses are performed offline following the case to avoid adding procedural time. See sections 6.3 to 6.6 for full details.
- Hemodynamic monitoring is routinely performed during ablation with an arterial line and pulmonary artery (PA) catheter (aka. Swann-Ganz Catheter). See sections 6.7 to 6.10 for full details. The pre-dantrolene arterial blood pressure mean right atrial, PA systolic, PA diastolic, mean PA pressure, and pulmonary artery wedge pressures will be recorded.
- Blood samples will also be drawn for calculation of a Fick cardiac output and for the pharmacokinetic (PK)/pharmacodynamic (PD) analysis. See section 6.12 for full details of the PK/PD analysis. A 2 mL sample from the femoral venous, arterial, and distal PA catheter will be collected.
- I.V. dantrolene will be administered over 3 minutes. Peak drug levels occur rapidly allowing the data collection protocol to proceed without delay.
- The post-dantrolene hemodynamics will be recorded.
- The post-dantrolene EP study with programmed ventricular stimulation will be repeated.

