- A 2 mL sample from the femoral venous, arterial, and distal PA catheter will be collected at 5, 10, 15, and 20 minutes post-dantrolene. The total amount of blood collected during the ablation is 30 mL.
- Respiratory mechanics (tidal volume, rate, minute ventilation) and an arterial blood gas (ABG) will be measured at 0, 10, and 20 minutes, and need for additional respiratory support will be assessed continuously as is standard care (see Section 6.13).
- The clinical and research activities will be complete, and the participant will leave the operating room awake, extubated, and hemodynamically stable.
- The participant will undergo baseline muscle (grip) and respiratory (NIF) strength testing in the post-op recovery area and an ABG will be measured 120 minutes after study drug was initiated

Encounter 3: Post-ablation Day 0-2.

- Following ablation, the participant will be returned to the EP holding room. It is clinical standard-of-care for patients to remain in the hospital at least overnight for monitoring. They will be under nursing observation and on continuous cardiac telemetry and oximetry. They will be on strict bedrest until post-operative Day #1 and they will be ambulated with assistance the morning after the procedure.
- 2 mL blood samples will be drawn at intervals of 4 to 12 hours for up to 48-hours during the post-ablation period. No more than 15 mL total will be drawn. We will use indwelling catheters whenever possible for blood collections. All patients will have indwelling catheters throughout the duration of study, and we do not anticipate needing to perform phlebotomy with a fresh stick during the study. See section 6.12 for full details.

- The research protocol is complete when the participant is discharged from the hospital.

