8.1 Data and Safety Monitoring Plan

The Data Safety Monitoring Board (DSMB) reviews safety data, study progress, and data quality. The DSMB is chaired by [name], MD (Professor of Pediatrics, Division of Pediatric Cardiology, Vanderbilt Children's Hospital) who is a clinical investigator and practicing cardiac electrophysiologist. Other members are [name], MD (Professor of Medicine, Director of the Division of Cardiac Electrophysiology, VUMC) who is a clinical researcher and has expertise in complex ablation including VT ablation; [name] who is an Anesthesiologist and clinical researcher (Associate Professor of Anesthesiology); and [name], MS (Senior Associate, Department of Biostatistics, VUMC) who has extensive prior experience as a DSMB statistician. The DSMB will review all serious adverse events (AEs). Any serious AE will be reported to the DSMB and IRB within 7 days from the investigators' awareness of the event. Any untoward medical event will be classified as an AE, regardless of its causal relationship with the study. The DSMB reviewed the results of the pilot study and provided input for the Phase II trial and recommended to proceed.

8.2 Reporting of Adverse Events or Unanticipated Problems involving Risk to Participants or Others

Adverse event reporting will utilize the NIH Common Criteria for Adverse Event Reporting (CTCAE version 5.0, published November 2017). It defines an adverse event (AE) as any unfavorable and unintended sign (including an abnormal laboratory finding), symptom, or disease temporally associated with the use of a medical treatment or procedure that may or may not be considered related to the medical treatment or procedure.

Adverse events include:

- Worsening (change in nature, severity or frequency) of conditions present at the onset of the trial
- Patient / subject deterioration due to the primary illness
- Intercurrent illnesses
- Drug interactions
- Events related or possibly related to concomitant medications
- Abnormal laboratory values or changes of vital signs, as well as significant shifts from baseline within the range of normal, which the Investigator considers clinically significant.

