Least inducible	0	No sustained VT/VF or NSVT
	1	1 episodes of NSVT with S4
↓	2	1 episodes of NSVT with S3
↓	3	1 episodes of NSVT with S2
↓	4	2 episodes of NSVT with S4*
↓	5	2 episodes of NSVT with S3*
↓	6	2 episodes of NSVT with S2*
↓	7	Sustained VT/VF with S4
Most inducible	8	Sustained VT/VF with S3
	9	Sustained VT/VF with S2

*the category assigned for 2 episodes of NSVT is based on the extrastimulus used to induce the second episode of NSVT.

Table 6. Secondary analysis of rhythm stability

	Category	
Least Stable	1	Ventricular Fibrillation
	2	Polymorphic VT
↓	3	Pleomorphic VT
↓	4	Unstable Monomorphic VT
Most Stable	5	Stable Monomorphic VT
	6	No Inducible VT/VF

safety concerns, and no adverse events have been observed, we planned the assessment of safety, which will be based on the frequency of adverse events. Other safety data such as blood pressure will be considered. All adverse events recorded during the study will be summarized. See Ethical Aspects of the Proposed Research for DSMB.

Respiratory Mechanics and Ventilation Endpoints: To monitor adequacy of ventilation, maintain safety, and measure the effect of dantrolene administration on ventilation, the anesthesiologist will monitor respiration and oxygenation as is standard of care for all patients during procedures and surgeries. The primary endpoint of the Respiratory Mechanics substudy is the incidence of the addition of respiratory support, including bag/mask ventilation, CPAP, BiPAP, LMA, or tracheal intubation, from the time of study drug administration until 120 minutes after study drug administration. Placement of airway support devices is at the discretion of the attending anesthesiologist and will be based on standard safety parameters such as oxygen saturation, adequacy of ventilation, and airway obstruction. Secondary endpoints include additional markers of respiratory mechanics and strength including negative inspiratory force, dynamometer measured grip strength, accelerometer (respiratory rate, tidal volume, minute ventilation), markers of gas exchange (arterial pH, pCO₂, pO₂, base excess), and electrolytes. Tidal volume, respiratory rate, and minute ventilation parameters will be continuously collected (recorded every minute) as available. We will summarize these data prior to study drug administration and at 10 and 20-minutes after dantrolene administration.

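### The adverse event comparison has no start at study drug, so ablation complications in patients who are still dosed can dilute pooled adverse event proportions

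*Combined protocol and SAP*

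**What the plan says.** Section 10.0 (Assessment of Safety) describes a safety assessment "which will be based on the frequency of adverse events" and adds: "All adverse events recorded during the study will be summarized". The DSMB interim analysis takes place "when 50% of the target enrollment is reached" and is meant "to test for an association between dantrolene or placebo and significant adverse events/harm". No onset window is attached to either.

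The definition of an event is broad. Section 8.1 says: "Any untoward medical event will be classified as an AE, regardless of its causal relationship with the study". Section 8.2 likewise covers events linked in time to a procedure as well as to a drug.

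The order of events is fixed. Consent is signed before the procedure (Section 5.0). Table 2 in Section 6.1 gives 60 to 140 minutes to the line "Clinical ablation procedure completed", ahead of the line for study drug. Section 6.2 confirms this: "Research activities will begin after completion of the ablation portion of the ablation procedure". Observation ends at discharge: "The research protocol is complete when the participant is discharged from the hospital".

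Three provisions bear on who reaches the comparison:

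- Section 5.0 allows for up to 20% withdrawal before randomization and names procedural complications as one reason.
- Section 9.0 says the PI may withdraw a participant who has an ablation complication before dosing.
- The safety analysis set in Section 10.0 requires receipt of dantrolene, which as worded leaves out placebo.

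**The concern.** An event that happened before the syringe was connected cannot have been caused by its contents. If a patient has a minor ablation complication, is judged stable and is dosed, the plan read literally counts that patient as an adverse event case whatever the drug does. On average this adds the same background to both arms. In a patient-level any-event or any-serious-event proportion, equal background shrinks the risk difference and, more strongly, the risk ratio.

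Event type alone does not sort this out. Table 3 lists headache under both drug and ablation, and tachycardia under the drug alongside atrial fibrillation, flutter or tachycardia under ablation. For such events only the onset time relative to dosing separates the two sources.

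The arms are small, so pre-dose events need not be balanced. A chance excess in either arm could mimic harm or hide it. What is at stake is how clearly the DSMB and the final report can read the adverse event comparison. No primary efficacy endpoint is involved.

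**Working it through.** **The plan's own figure.** Section 10.0 enrols up to 105 to allow for 20% withdrawal before study drug: 84 / (1 − 0.20) = 105, which reproduces. It implies 105 − 84 = 21 exits before dosing. Some of these will be patients with complications, so they do not enter a comparison of dosed patients. The documents give no adverse event rate and no power for the adverse event comparison.

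**Inputs from the documents.** 56 dantrolene and 28 placebo (Section 10.0). For the interim I take 42 dosed patients, 28 vs 14. This follows from half of 84, and equally from half of 105 enrolled with 20% lost: 105 × 0.5 × 0.8 = 42.

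**Assumptions.** Post-dose risk p of any event: 35% dantrolene, 10% placebo. A share b of dosed patients in each arm has a pre-dose event, independent of post-dose events. Test: Fisher's exact, two-sided 5%. The plan does not state a level for the adverse event test.

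**Formula.** The any-event proportion in an arm is b + (1 − b)p, so the risk difference is (1 − b)(0.35 − 0.10). For b = 5%:

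- dantrolene: 0.05 + 0.95 × 0.35 = 0.3825
- placebo: 0.05 + 0.95 × 0.10 = 0.145
- difference: 23.75 points
- ratio: 0.3825 / 0.145 = 2.64

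| Pre-dose share b | Dantrolene | Placebo | Risk difference (points) | Risk ratio | Power, 56 vs 28 | Power, 28 vs 14 |
|---|---|---|---|---|---|---|
| 0% | 35.0% | 10.0% | 25.0 | 3.50 | 71% | 36% |
| 2% | 36.3% | 11.8% | 24.5 | 3.08 | 67% | 34% |
| 5% | 38.25% | 14.5% | 23.75 | 2.64 | 60% | 32% |
| 10% | 41.5% | 19.0% | 22.5 | 2.18 | 51% | 28% |

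**Other assumed risks.** With 40% vs 10%, Fisher power at 56 vs 28 falls from 85% (b = 0) to 75% (5%) and 66% (10%). With 30% vs 10% it falls from 52% to 43% and 36%. The direction is the same throughout.

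**Chance imbalance.** The standard deviation of the between-arm difference in pre-dose proportions is √[b(1 − b)(1/28 + 1/56)]. At b = 5% this is √(0.0475 × 0.0536) = 0.050, or 5 points. At 28 vs 14 it is √(0.0475 × 0.1071) = 0.071, or 7 points. Either sign is possible.

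**The case against.** The case on the other side is substantial, and most of it narrows the point.

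*Pre-dose complications are largely removed.* A reader might infer that every ablation complication counts in both arms. The documents do not support that. Sections 5.0 and 9.0 let such patients leave before randomization or dosing, and the safety set requires receipt of drug. Serious complications are the ones most likely to end participation, so the background for the interim test on significant events may be small. What survives is that Section 9.0 says may, not must, so the share need not be zero.

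*Only one adverse event test is expressly stated.* That is the interim one. The main sentence on adverse events promises a summary. A final significance test could only be inferred from the general remarks on categorical data.

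*Other harm measures are already anchored.* A reader might infer that any drug harm is diluted, or that this is the only look at harm. Neither holds. Added respiratory support is counted from study drug to 120 minutes after it. Cardiac index and PA diastolic pressure are tested two-sided with adjustment for pre-drug values, expressly to allow for negative inotropy. In a table by event type, flushing, somnolence or muscle weakness would be little diluted by ablation complications. If events rather than patients are counted, the absolute difference is noisier but not biased.

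*Causality grading uses timing.* In Section 8.2 a likely grade requires onset during or after study treatment, or worsening. That is investigator attribution. Nothing limits the frequency comparison to that grade.

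*The text may be incomplete.* Section 10.0 refers to a section on ethical aspects for the DSMB, which is not in the supplied text. An onset rule could be there; none appears in what is supplied.

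**Conclusion.** The point holds in a limited form. As written, the adverse event summary and the interim comparison have no start at study drug, so ablation complications in patients who are nevertheless dosed count as cases. The effect falls on pooled any-event or any-serious-event proportions and on event types shared with ablation. It does not reach the respiratory-support endpoint or the baseline-adjusted hemodynamic tests, and it hardly touches drug-specific events.

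The size depends on a pre-dose rate that the documents do not give. Under the assumed 35% vs 10%, the loss of power at full size is about 4 percentage points at a 2% pre-dose share, 11 at 5% and 20 at 10%. At the interim the loss is at most 8 points over that range, because power starts at only 36%: there, the number of patients is the main limit. These figures treat the outcome as one pooled binary event per patient and assume that placebo recipients belong in the safety set, which its present wording does not say. This is an inexpensive improvement to the safety analysis, best made before the interim.

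**What to change.** In Section 10.0 and in the DSMB interim report:

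1. Compare arms on adverse events with onset, or worsening in grade, at or after the start of study drug and through discharge.
2. List events that began before study drug separately, as procedural events.
3. Record each event's onset relative to the start of study drug.
4. Word the safety set as all randomized participants who received dantrolene or placebo, analysed by treatment received, so that the stated comparison has a control arm.

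The cost is one onset-time field, revised SAP and DSMB wording, and a little more analysis work. No new data source or visit is needed.
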